treatment (1.0), the number of persons needed to include is 50 persons per condition to reach for 80% power. Expecting a dropout rate of 25%, we will include 63 persons per arm, for 4 arms a total of 252 adult patients with PTSD and - at least 4 - PD symptoms. Of these patients, 80 next to 40 healthy matched controls will be asked for additional MRI research before and after treatment. In total, 292 persons will be included in this study.

Intervention: In patients with PTSD and BPD: EMDR (3-6 months plus 6-9 months treatment pause) compared to integrated DBT-EMDR (12 months); in patients with PTSD and CPD: ImRs (3-6 months plus 6-9 months treatment pause) compared to integrated ImRs-SFT (12 months).

Main study parameters/endpoints: Primary outcome measure is PTSD symptom severity after 12 months. Secondary outcome measures are PD symptoms (SCID-5-PD), disability (WHODAS), quality of life (EQ-5D-5L) and health costs (Tic-P). At baseline (T₀) and after 12 months (T₄) clinical interviews (CAPS-5, SCID-5-PD dimensional score) and self-rating scales (PCL-5) will be used. After 3 (T₁), 6 (T₂), 9 (T₃), and 18 months (follow-up), questionnaires only will be used. At baseline, candidate predictors will be measured including above mentioned cognitive, affective, relational factors, and hormonal and epigenetic factors. In a subgroup, structural and functional MRI, with resting-state and an emotion processing (face recognition) will be performed.

Nature and extent of the burden and risks associated with participation and benefits:

The burden and risks associated with participation in this study is reasonable. All patients will receive psychotherapy, which is considered to be the most effective treatment for PTSD and PD. There is evidence that all four conditions are therapeutic in patients with PTSD and PD and no evidence yet what condition is more effective. Total time of the six measurements is approximately 5 hours per patient for interviews and 5 hours for questionnaires (see table 3), which are partly part of the routine outcome measurements (ROM). Questionnaires can be filled in at home. On the one hand, extensive clinical interviews and self-rating scales can be felt as disturbing because of fatigue, taken time and emotional burden. On the other hand, patients may feel well recognized by the time taken by specialized clinicians for them. Assessors will be well-trained and work in close

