Integrated PTSD-PD treatment consist of a PTSD treatment interwoven in a PD treatment that takes at least twice sessions per week, for the duration of one year:

- DBT (Dialectical Behavior Treatment), a manualized outpatient cognitive-behavioral treatment with two components: (a) weekly individual therapy and (b) weekly group skills training. Individual sessions focus on a hierarchy of target behaviors, which the patient tracks on a daily basis with diary cards. Behavioral analyses of the pattern and chain of thoughts, emotions, and events take place routinely to help the patient identify triggers and alternative strategies for coping. Change strategies such as problem solving and reinforcement techniques are used in combination with acceptance and validation of the patient's experience. Group skills' training is used to help patients develop less self-destructive and more adaptive means of coping with intolerable affects. These skills include awareness of emotions and reactions, interpersonal effectiveness, emotion regulation, and distress tolerance. Skills are then integrated into the individual treatment in problem situations, e.g. suicidal urges (Linehan, 1993).

- SFT (schema focused treatment) is a form of psychotherapy integrating cognitive therapy, behavior therapy, object relations, and gestalt therapy into one unified,

systematic approach to treatment. The focus in SFT is on changing maladaptive schemes that patients develop early in life and thereby improve emotion regulation skills. Change is achieved through a range of behavioral, cognitive, and experiential techniques that focus on (1) the therapeutic relationship, (2) daily life outside therapy (also through homework assignments), and (3) past (traumatic) experiences (Young et al., 2003). Psychomotor therapy (PMT) is part of the SFT treatment protocol.

[figure not shown]
In the Sinai Centrum, 2 “Zorgpaden” will be implemented in Fall2017:

“Zorgpad 1” with EMDR or ImRs (3-6 months) and Zorgpad 2” with EMDR-DBT or ImRs - SFT (9-12 months). Therapists need to be “adherent-to-the model”, which will be ascertained by regular supervision with audiovisual recordings based on the different theoretical psychotherapeutic principles and therapies are delivered by protocol. At this moment, there is no clear scientific evidence and criteria are not explicitly defined for the one or the other treatment, except that patients with PTSD without comorbid PD have to be indicated for “Zorgpad” 1.

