4. STUDY POPULATION

4.1 Population

The study population consists of all patients between 18-65 years old, referred to the SC with comorbid PTSD and PD, who are willing to participate in the study (informed consent); N = 252 patients (see 4.4), of which sub-group of 80 patients (N = 40 Condition 1 + 40 Condition 2) will participate in the MRI study (before and after treatment). For baseline MRI comparison, extra 40 healthy controls, matched on age, gender and educational level, will be recruited also for the MRI study via advertisements in local newspapers and through hersenonderzoek.nl. In total, 292 persons will be included in this study.

A pilot episode will be introduced (September – December 2017) to test the feasibility of the study and inclusion rate. Feasibility is enhanced by the opportunity to build on the established expertise of the academic research group in Arkin – Research and VUmc in conducting effect studies, longitudinal and neurobiological studies.

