⊗ Timing of the T2 measurement will be directly after trauma treatment, around 6 months

#The SCID-5-P at T0 is part of the regular intake procedure at the Sinai Centre

Table 2: Overview of add-on cognitive task, biological measurements, including MRI

MEASUREMENTS		DURATION	To	T1	T2	T3	T4	FU
in months			0	3	6 [⊗]	9*	12	18
COGNITIVE TASKS AT DAY 2		10 min						
Working memory	N-back	10	X*					
Interference	Stop/Signal task	15	X*					
PHYSICAL EXAMINATION AT DAY 2		30 min						
Body measures	Weight, height	10	X					
Blood pressure	Systolic and diastolic	5	X					
HPA axis (Hair)	Hair sample (cortisol)	5	X		X			
Biomarkers	Fasting blood sample (5HTTLPR, BDNF, FKBP5, oxytocin/OXTR) & Full blood	10	X		X			
MRI SESSION IN SUBSAMPLE WITHIN 2 WEEKS		60 min						

Functional MRI	Face recognition task	15	X		X			
Structural MRI		7	X		X			
Resting state MRI		10	X		X			
DTI		10	X		X			

DTI = Diffusion Tensor Imaging, MRI = Magnetic Resonance Imaging.

[&] Timing of the T2 measurement will be directly after trauma treatment, around 6 months

* Timing of the T3 measurement will be 3 months after T2, around 9 months

Table 3: Overview of duration of measurements (in minutes)

	To	T1	T2	T3	T4	Follow-up
Interviews	45	-	45	-	195	-
Questionnaires	91	15	88	15	88	27
n-back	10	-	-	-	-	-
TOTAL	141 (ca. 2.5 hrs)	15	128 (ca. 2 hrs)	15	278 (ca. 4,5 hrs)	27
Blood/hair	30	-	30	-	-	-
MRI	90	-	90	-	-	-
TOTAL for subgroup with MRI/blood/hair	261 (ca. 4 hrs)	15	218 (ca. 3,5 hrs)	15	278 (ca. 4,5 hrs)	27

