Blood samples will be collected in 3 x 6ml tubes and the frozen samples will be stored at -80°C for intended future assaying of inflammatory markers (see Coelho et al., 2014), neuropeptides (such as oxytocin, 5HT), and epigenetics (such as FKBP5-methylation, OXTR- & 5HTTLPRgenes). The tubes will be stored without personal data linked to it, and they will only be marked with a subject number as described in section 9.1. below. Cortisol level (HPA-indicator) will be assessed in hair. This sample can be collected non-invasively by cutting a 1-cm distal to the scalp (1 month's exposure) sample of hair (Russell et al., 2012). All samples will be stored for 15 years (according to Archiefwet 1995).

In a subgroup: MRI session

Exclusion criteria for MRI research will be checked (metal implants, pregnancy, somatic disorders interfering with brain functioning, other (psycho-)pharmaca than at-least-3-months stabile dose SSRI or low-dose benzodiazepines, claustrophobia). A separate visit for MR scanning will be planned within 2 weeks of To, before the start of treatment, without causing a delay in treatment start. MRI sessions take at maximum 60 minutes (30-min functional MRI with a face recognition, and a suppression vs. reappraisal task, 5-min structural MRI, 8-min resting state MRI; and 8-min DTI) plus 30 min preparation. Next to patients, 40 healthy control persons, matched for age, gender, and education, will be asked to participate in one MRI session (no repeat MRI). These healthy control persons will be recruited via advertisements in local papers.

T1, T3 and FU

Patients do not have to come to the study center for T1, T3 and FU and can fill in the questionnaires via a login code at home if they have access to the internet (see Table 1.). Child trauma and life events questionnaires are only done at baseline (CTQ, LEC-5). Total duration of these measurements (T1, T3 and FU) will be between 15 and 30 minutes (see Table 3).

T2 visit

From all participants whose blood and hair was collected at baseline, blood and hair will be collected at T2 as well (duration 30 minutes). All participants who participated in the fMRI study at baseline will have their second MRI at T2. (duration 90 minutes). At T2, the CAPS-5 will also be conducted and participants will fill out the same questionnaires as at T0, except for the CTQ and LEC-5. Total duration of these measurements of will be ca. 2 hours (see Table 3).

Extra contact moment

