- Neurobiological factors: Neural factors (smaller ACC and hippocampus volume, increased right amygdala and ventral ACC activity and de/increased dorsal ACC activity), and Hormonal/ epigenetic factors (5-HTTLPR, BDNF, cortisol/FKBP5-methylation, oxytocin/OXTR).

Questions that will be answered with machine learning in this study are:

1. Does brain activity predict treatment outcome for PTSD and PD (all treatment conditions together; N = 80)
2. Does brain activity predict treatment outcome for PTSD (EMDR and ImRs; N = 40)
3. Does brain activity predict treatment outcome for integrated PD/PTSD treatment (EMDR + DBT and ImRs + SFT, N = 40)
4. Data from the MRI at T2 can be used to predict relapse after treatment for all treatments together (N = 80 if all patients return for a second MRI) or for trauma treatment and integrated treatment separately (N = 40 for both).

fMRI data will be analysed with Statistical Parametric Mapping (SPM) software or FMRIB Software Library (FSL) to map connectivity in the brain. Standard group comparisons will be used to analyse structural and task-related (face recognition) fMRI. First, ANOVA analyses will be performed with patients vs. controls for baseline comparison. Second, full factorial analyses will be conducted in patients-only, with time (baseline vs. end of treatment) and condition (type of treatment) as factors to analyse the effect of treatment on (task-related) brain structure, connectivity and activity. Independent component analysis (ICA; FSL MELODIC) and dual regression analyses will be used to study changes in functional connectivity of brain networks (with a focus on the salience

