network, negative affect network, ventral and cognitive control network). Brain areas that fluctuate simultaneously over time in blood-oxygen level dependent (BOLD; proxy for brain activity) response are automatically assigned to a component per subject. After filtering and preprocessing of the components (e.g. components that are caused by movement or scanning artefacts), these components are averaged across groups. Through non-parametric permutation testing (FSL randomise) we compare functional connectivity of these networks between intervention groups and over time (T₀ to T₂). For the whole-brain network analyses, the structural MRI will be parcellated into 92 regions of interest (ROIs), based on the Automated Anatomical Labeling (AAL) atlas. These parcellations will be transformed to resting-state fMRI and time series are extracted for each ROI and correlated to get a whole-brain connectivity matrix per subject. The brain connectivity toolbox (BCT) will be used to calculate network topological indices (e.g. modularity, betweenness centrality, clustering coefficient and efficiency) from these matrices. Network topological indices narrow down the large amount of information from the brain scans to a few neurobiologically meaningful measures (Rubinov & Sporns, 2010). A more detailed description of these topological measures can be found in Bullmore and Sporns (2009). These measures will be calculated for every condition and compared through permutation-testing.

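### The second MRI (T2, about month 6) is analysed as an end-of-treatment scan and used to predict relapse, although the integrated arms are only 50% to 67% through their treatment.

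*Combined protocol and SAP*

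**What the plan says.** Section 4.1 plans an MRI subgroup of 80 patients, 40 per condition, who "will participate in the MRI study (before and after treatment". The Summary describes the scans in the same way. Section 5.3 fixes the second scan: "All participants who participated in the fMRI study at baseline will have their second MRI at T2". Table 2 shows MRI at T0 and T2 only, and its footnote defines the visit: "Timing of the T2 measurement will be directly after trauma treatment, around 6 months".

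In the Summary the integrated arm for borderline patients is "compared to integrated DBT-EMDR (12 months", with the same duration for the cluster C arm. Section 3 says integrated treatment "takes at least twice sessions per week, for the duration of one year", but its description of the care pathways gives 9 to 12 months. The PTSD treatments are 12 to 18 sessions over no more than 6 months (section 3), followed by a pause of 6 to 9 months (Summary).

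In section 7.1 the full factorial analysis in patients uses "time (baseline vs. end of treatment) and condition (type of treatment) as factors". The connectivity analysis in the same section labels the interval differently: "we compare functional connectivity of these networks between intervention groups and over time (T₀ to T₂". Machine-learning question 4 adds: "Data from the MRI at T2 can be used to predict relapse after treatment for all treatments together". As an alternative it offers separate models for trauma treatment and integrated treatment, with 40 patients each. No section defines relapse or gives its time window.

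**The concern.** One scan carries two meanings. For the PTSD-only arms T2 is the end of treatment. For DBT-EMDR and SFT-ImRs it falls within the course, and no later scan is planned. A time-by-condition result labelled as end of treatment would present a part-delivered integrated course as a finished one. In particular, a null interaction could be reported as showing that integrated treatment changes the brain no more than PTSD treatment alone, when a third to a half of the integrated course had still to be given.

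The relapse question has a related problem. After T2 the PTSD-only arms enter the planned pause, while the integrated arms continue with sessions at least twice a week. Pooling the arms from T2 onwards mixes symptom return off treatment with symptom course on treatment. With no definition of relapse and no window, the text does not keep the two apart.

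**Working it through.** **Inputs**

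- Second scan at T2, about month 6: section 5.3 and Table 2.
- T4 at month 12 and follow-up (FU) at month 18: section 3.
- Integrated course of 12 months (Summary; one year in section 3) or 9 to 12 months (care pathways, section 3). I carry both ends of the range.
- PTSD-only treatment taken to end at month 6. Section 3 itself places T4 six months after that pathway is completed.
- MRI subgroup of 80, 40 per condition: section 4.1.
- About 40 second scans expected and 160 scan sessions in all: section 4.4.
- CAPS-5 at T0, T2 and T4; PCL-5 at every visit including FU: Table 1.

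**The plan's own figure.** Scan sessions = 80 patients at baseline + 40 controls + 40 repeat scans = 160, which matches section 4.4. If all 80 patients returned, as section 5.3 implies, the total would be 80 + 40 + 80 = 200.

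**Timeline.** Share of course delivered at T2 = 6 / course length in months, and months after treatment at a visit = visit month − end of treatment.

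| Arm | End of treatment (month) | Share of course at T2 | Months after treatment at T4 | Months after treatment at FU |
|---|---|---|---|---|
| PTSD-only | 6 | 100% | 12 − 6 = 6 | 18 − 6 = 12 |
| Integrated, 9 months | 9 | 6/9 = 67% | 12 − 9 = 3 | 18 − 9 = 9 |
| Integrated, 12 months | 12 | 6/12 = 50% | 12 − 12 = 0 | 18 − 12 = 6 |

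The interval from T2 to T4 is 12 − 6 = 6 months. Integrated patients are in treatment for all 6 of those months on a 12-month course, and for 3 of the 6 on a 9-month course.

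**Share of patients affected.** Integrated patients are 40/80 = 50% of the planned MRI subgroup. Section 4.4 expects only about 40 second scans and gives no split by arm. An even split, which is my assumption, would leave 40/2 = 20 per treatment type.

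**Measures after treatment.** With a 12-month course, T4 coincides with the end of integrated treatment, so those arms have no CAPS-5 after treatment. They do have PCL-5 at FU, 6 months later. With a 9-month course, the CAPS-5 at T4 falls 3 months after treatment.

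**The case against.** The strongest defence is that T2 was chosen as a common anchor at the end of the trauma component in every arm. Project B in section 5.3 is about predictors of PTSD treatment and asks whether PTSD treatments work through extinction of fear responses. Scanning all arms when that component ends suits the question, and the visit timing is stated openly. This stands as a justification of the T2 scan. It does not rescue the label: the factor it is crossed with is type of treatment, and question 4 names integrated treatment as a whole.

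A reader might infer that the T0-T2 comparison is invalid. The documents do not support that. Both groups are scanned at the same nominal time, so the contrast is a sound randomised comparison at about 6 months.

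A reader might also infer that integrated patients cannot relapse after treatment within the trial. That would need a T2-T4 window, which section 7.1 does not set. PCL-5 at 18 months observes these patients after treatment, and on a 9-month course T4 does so too.

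Nor are the PTSD-only arms certain to be off treatment after T2. Section 3 allows further treatment when acutely needed, and allows SFT or DBT after T4.

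Finally, the pooled model is optional and section 7.1 already lists the by-treatment models. A T2 brain feature that differs by arm would pass for a relapse predictor only if relapse risk also differed by arm and arm were left out of the model, and the plan does not say that it would be left out.

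**Conclusion.** The inconsistency is real and can be read directly from the documents. The second scan is at T2 for everyone, and integrated treatment is then 50% to 67% delivered, depending on which stated duration applies. Describing that scan as the end of treatment, or as following treatment, is wrong for 40 of the 80 planned MRI patients. This is half of the MRI subgroup, not half of the 252 trial patients. The T0-T2 contrast can be kept, but it supports no conclusion about completed integrated treatment. Pooled relapse prediction from T2 has no single meaning across arms.

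A reader might go further and infer that brain effects in the integrated arms are halved at T2. The documents give no effect size and no time course for the MRI measures. If the effect built up linearly, which is an assumption, the share visible at T2 would be 50% to 67%. That is an illustration only and the conclusion does not depend on it.

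The primary CAPS-5 analysis and the sample size are not affected.

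**What to change.** 1. In section 7.1, rename the time factor *T0 versus T2 (end of trauma-focused phase; integrated treatment ongoing)*. State there that the time-by-condition contrast supports no conclusion about completed integrated treatment.
2. Bring the Summary and section 4.1 into line with section 5.3, Table 2 and the T0-T2 wording already used for connectivity in section 7.1. Reconcile the stated integrated durations (12 months versus 9 to 12 months).
3. In question 4, drop the pooled model and use the by-treatment models already listed. Define relapse, and count it from each arm's own end of treatment:
   - PTSD-only arms: T2 to T4 and to follow-up, recording any further treatment given under section 3, including SFT or DBT started after T4.
   - Integrated arms: T4 to the 18-month follow-up on PCL-5, because no CAPS-5 is done at follow-up. Say that the predictor is a scan taken during treatment.
4. Report the T2-T4 course in the integrated arms separately, as course under continuing treatment.

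The cost is wording and a relapse definition, with no added scans or visits. The relapse models become smaller: at most 40 per treatment type, and about 20 if only 40 second scans are obtained and they split evenly. Relapse in the integrated arms would rest on self-report, and the MRI claim becomes narrower.

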7.2 Secondary study parameters

Secondary study parameters are quality of life with WHODAS, EQ-5D-5L, and health care consumption with Tic-P. The secondary analyses on these continuous measures will be similar to the primary analyses.

